### **C. Gastrointestinal Disturbance**

Gastrointestinal disturbances (nausea, diarrhea, anorexia, vomiting, constipation, and abdominal pain) have been reported in the subjects treated with XL888, but especially with the subjects who received the PIB formulation. Some of this may be attributed to the effects of the polyethylene glycol in the vehicle; however, multiple histopathological findings were present in multiple tissues of the GI tract (esophagus, glandular and nonglandular stomach, duodenum, jejunum, ileum, cecum, colon, and rectum) in the preclinical studies as well. Gastrointestinal tract histopathologic changes correlated with increases in peripheral neutrophil counts in both rats and dogs and were suggestive of a generalized inflammatory reaction in response to tissue injury.

Diarrhea was the most frequent gastrointestinal disturbance on Study XL888-001. Subjects should be instructed to notify their physician immediately at the first signs of poorly formed or loose stool or an increased frequency of bowel movements.

1. Administration of antidiarrheal agents (example Imodium or Lomotil) is recommended as initial management. Dietary modifications may be helpful. Some subjects may require concomitant treatment with more than one antidiarrheal agent. General supportive measures should be implemented including monitoring for and correction of fluid and electrolyte abnormalities.
2. It is also recommended that nausea and vomiting be treated as indicated with supportive care and anti-emetics.

### **D. QTc Interval Prolongation**

In vitro evaluation of XL888 using manual patch-clamp electrophysiology showed that XL888 inhibits HERG channel activity with an IC50 value of 5.6  $\mu$ M, which translates to a safety factor of  $\sim 298$  (Redfern et al. 2003) assuming a plasma Cmax of 474 ng/mL (0.94  $\mu$ M) and approximately 98% plasma protein binding. This estimated safety factor is substantially higher than the threshold for concern recommended by Redfern et al (ie, 30-fold), suggesting a low risk of risk of developing QTc interval prolongation at current dose levels. The potential for EXEL-4633 (ie, the primary metabolite of XL888) to prolong the QTc interval has not been evaluated in vitro. Guidelines for management of corrected QT prolongation are as follows:

If a subject on study has a QTc interval increase by  $\geq 60$  ms to an absolute value  $> 470$  ms or an increase to an absolute value of  $> 500$  ms at any evaluation, and if the subject is

asymptomatic (does not have palpitations, dizziness, syncope, orthostatic hypotension, a significant ventricular arrhythmia on electrocardiogram (ECG), or a change in vital signs), the following actions should be taken:

- Hold XL888 dosing
- Check electrolytes, especially magnesium and potassium; correct abnormalities as clinically indicated
- Repeat ECGs hourly until the QTc is < 30 ms increased over the average baseline value

Subjects with QTc prolongation and symptoms should be monitored closely. Cardiology consultation is recommended for evaluation and subject management.

No additional XL888 should be given to the subject until after the event has resolved. If any additional XL888 is given, it should be at a reduced dose.

### **5.3.3 Timing of Dose Administration**

Trial treatment should be administered on Day 1 of each cycle after all procedures/assessments have been completed as detailed on the Trial Flow Chart (Section 6.0). Trial treatment may be administered up to 3 days before or after the scheduled Day 1 of each cycle due to administrative reasons.

All trial treatments will be administered on an outpatient basis.

**Pembrolizumab** 200 mg will be administered as a 30 minute IV infusion every 3 weeks. Given the variability of infusion pumps, a window of -5 minutes and +10 minutes is permitted (i.e., infusion time is 30 minutes: -5 min/+10 min).

The Pharmacy Manual contains specific instructions for the preparation of the pembrolizumab infusion fluid and administration of infusion solution.

**XL888** will be administered twice weekly (days 1 and 4) orally starting on day 1 of every 3-week cycle.

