## 2.0 TRIAL DESIGN

Open label phase I trial. Primary objective is to determine the recommended phase 2 dose (RP2D) of the combination of XL888 and pembrolizumab. The design is 3+3 with 3 dose levels of XL888 (X). MTD is defined as the dose at which less than one-third of the subjects experience a DLT in the first 4 weeks of treatment.

After determining the RP2D, an additional 16 patients with pancreatic cancer (Arm A) and 16 patients with colorectal cancer (Arm B) will be enrolled in an expansion phase to confirm toxicity profile and obtain paired biopsies. Paired biopsy performed on 8 patients in each group. Patient selected for biopsy must have a primary or metastatic non-bone site that is amenable to safe biopsy. Bone only lesions are not suitable for biopsy. Patients undergoing paired biopsies will be assigned into two treatment cohorts (8 in each) and treated according to the schema below.

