### **Rationale for pembrolizumab dose selection/regimen/modification**

An open-label Phase I trial (Protocol 001) was conducted to evaluate the safety and clinical activity of single agent MK-3475. The dose escalation portion of this trial evaluated three dose levels, 1 mg/kg, 3 mg/kg, and 10 mg/kg, administered every 2 weeks (Q2W) in subjects with advanced solid tumors. All three dose levels were well tolerated and no dose-limiting toxicities were observed. This first in human study of MK-3475 showed evidence of target engagement and objective evidence of tumor size reduction at all dose levels (1 mg/kg, 3 mg/kg and 10 mg/kg Q2W). No MTD has been identified to date. 10.0 mg/kg Q2W, the highest dose tested in PN001, was the dose and schedule utilized in Cohorts A, B, C and D of this protocol to test for initial tumor activity. Recent data from other clinical studies within the MK-3475 program has shown that a lower dose of MK-3475 and a less frequent schedule may be sufficient for target engagement and clinical activity.

PK data analysis of MK-3475 administered Q2W and Q3W showed slow systemic clearance, limited volume of distribution, and a long half-life (refer to IB). Pharmacodynamic data (IL-2 release assay) suggested that peripheral target engagement is durable (>21 days). This early PK and pharmacodynamic data provides scientific rationale for testing a Q2W and Q3W dosing schedule.

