**Dose level 3 will only be tested if we observe 2 DLT's on dose level 2.**

### 5.2.2 Dose Escalation

Starting dose of 45mg; if  $\geq 2$  patients with DLTs in 3 ( $\geq 2/3$ ) or 6 ( $\geq 2/6$ ) subjects; stop and consider reduced dose of XL888. If not, increase dose to 90 mg and test 3-6 patients. If  $\geq 2$  patients with DLTs in 3 or 6 subjects, reduce dose to 60 mg and try again. If an acceptable dose is identified, treat 16 more patients at the MTD. Prior to dose escalation, we will obtain approval from the Data Safety and Monitoring Committee (DSMC).

**5.2.3 Dose limiting toxicity (DLT)** will be defined as any of the following definitely treatment related adverse events during the first 21 days of therapy:

- Grade IV neutropenia lasting more than 8 days; any neutropenic fever or sepsis;
- Grade III with clinically significant bleeding or any grade IV thrombocytopenia;
- Grade III nausea, vomiting, or diarrhea, lasting  $>72$  hours despite adequate supportive care;
- Other non-hematologic treatment-related toxicity at Grade III or higher
- Grade 4 asymptomatic laboratory abnormalities that last for more than 24 hours or Grade 3 asymptomatic laboratory abnormalities lasting more than 21 days is a DLT.
- Grade IV or higher diarrhea, nausea, vomiting
- In ability to take more than 75% of XL888 due to toxicity.

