### **5.7.2 Subject Replacement Strategy**

Patients who do not complete the intended course of chemotherapy due to reasons other than toxicity will be considered as in-evaluable for the primary endpoint and will be replaced.

[illegible]

Trial Period:	Treatment Cycles a									End of Treatment	Post-Treatment		
Treatment Cycle/Title:	Main Study Screening (Visit 2)	1	2	3	4	5	To be repeated beyond 8 cycles			Discon	Safety Follow-up	Follow Up Visits b	Survival Follow-Up
Scheduling Window (Days):	-28 to -1	± 3	± 3	± 3	± 3	± 3	± 3	± 3	± 3	At time of Discon	30 days post discon ± 7 days	Every 8 weeks post discon	Every 12 weeks
Comprehensive Serum Chemistry Panel	X	X	X	X	X	X	X	X	X	X	X	X	
Fasting triglyceride, cholesterol and glucose	X			X				X					
Urinalysis	X			X				X		X			
T3, FT4 and TSH	X		X			X			X	X	X		
ECG g	X	X	X		X		X g		X g				
Tumor Imaging	X f			X h			X h						
Archival or Newly Obtained Tissue Collection i	X	X											
Correlative Studies Blood Collection j	X	X	X	X						X			

- Treatment cycles are 3 weeks
- Only for patients with ongoing treatment related toxicities
- Pembrolizumab will be given day 1, XL888 twice weekly orally
- ECOG performance status should be done within 10 days or less from day 1 of cycle 1
- Ophthalmologic exam done at baseline and repeated only if there are symptoms
- Baseline imaging with 8 weeks of day 1 is acceptable
- ECG day1 2 to 3 hours after administration of XL888 every other cycle after C2 (C1, C2, C4, C6 etc)
- Scans will be done every 3 cycles between day 15 and day 21
- Paired biopsies will only be obtained from 16 patients on the dose expansion cohort
- Samples will be collected at baseline, day 15, and every cycle for the first 9 weeks. Analysis will include proportion of T, B, NK, memory and effector T cell subsets and expression of PD-1, PD-L1 and B7 family members. Samples will be collected at baseline and on weeks 6 and 9. This will be performed using interferon- gamma and CD107.

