#### **7.1.4.2 Treatment Period**

##### **7.1.4.1 Day 1 ( $\pm 3$ days) of each cycle**

- Record concomitant medications
  - Vitals (temperature, HR, BP and RR)
  - History and physical exam, pill diary (prior cycle see section 11.4) and pill count (prior cycle)
  - ECOG performance status
  - Toxicity assessment
  - 12 lead ECG after XL888 administration in cycle 1, cycle 2 and every other cycle
    - Laboratory Assessments

- Hematology hemoglobin, hematocrit, red blood cell count, white blood cell count with differential and platelet count
  - Chemistry sodium, potassium, chloride, bicarbonate, magnesium, calcium, phosphorus, blood urea nitrogen, creatinine, glucose (random), total bilirubin, LDH, total protein, ALP, ALT, AST, and albumin
  - Tumor markers - when applicable
  - Fasting Lipid profile every 3 cycles starting Cycle 4 (i.e C4D1, C7D1, C10D1, C13D1 etc)
  - Urinalysis every 3 cycles starting Cycle 4 (i.e C4D1, C7D1, C11D1 etc)
    - T3, FT4, TSH cycle 2 and then after every 3 cycle
    - For the cycle 1 day 1 labs, blood samples from the screening tests maybe used if completed within 1 week of day 1
- Blood sample 20 cc for correlative work (only cycle 1, 2, 3)
  - Pembrolizumab 200 mg will be administered as a 30 minute IV infusion every 3 weeks. Given the variability of infusion pumps, a window of -5 minutes and +10 minutes is permitted (i.e., infusion time is 30 minutes: -5 min/+10 min).
- XL888 will be administered orally in the infusion center (first dose of each cycle only) prior to pembrolizumab. **(in selected case in patients receiving paired biopsies XL888 will be held in cycle 1)**

#### 7.1.4.2 Days 4, 8, 11, 15 and 18

- XL888 dose administered and diary completed

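### The optional 3-day early start can put XL888 doses 1 or 2 days apart and, in dose escalation, brings cycle 2 doses into the 21-day DLT window

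*Combined protocol and SAP*

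**What the plan says.** Section 5.3.3 sets the window: "Trial treatment may be administered up to 3 days before or after the scheduled Day 1 of each cycle due to administrative reasons". The flow chart in Section 6.1 and the Day 1 visit heading in Section 7.1.4 repeat the 3 days either side.

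The same section says that XL888 "will be administered twice weekly (days 1 and 4) orally starting on day 1 of every 3-week cycle". Section 7.1.4 lists the dosing days after Day 1 as "Days 4, 8, 11, 15 and 18", and the pill diary in Section 11.4 has two entries for each of three weeks. Section 7.1.4 also ties XL888 to the clinic visit: "XL888 will be administered orally in the infusion center (first dose of each cycle only) prior to pembrolizumab". When Day 1 moves, the first XL888 dose moves with it.

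Section 5.2.3 counts DLTs as "definitely treatment related adverse events during the first 21 days of therapy". Section 2.0 instead defines the MTD by patients who "experience a DLT in the first 4 weeks of treatment". That conflict is a separate matter, so both windows are checked below.

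**The concern.** The window and the XL888 calendar collide at the end of a cycle. The last XL888 dose is due on Day 18 and the next cycle may start on Day 19. Both instructions stand, and no legible text sets a minimum interval between XL888 doses or says what happens to the Day 18 dose. A site that follows the text as written can give doses on consecutive days.

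In dose escalation there is a second consequence. The first cycle 2 doses may be given before the 21-day DLT observation is complete. Cohorts are 3 to 6 patients, and two DLTs stop escalation or send the dose down (Section 5.2.2). Patients at the same dose level should have the same planned exposure over the period in which DLTs are counted. Here a scheduling convenience can change it.

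**Working it through.** **Inputs.** Cycle length is 21 days, so the scheduled cycle 2 Day 1 is Day 22. The window of 3 days either side allows a start S on Days 19 to 25. Days 1 and 4 of each of three weeks give XL888 on Days 1, 4, 8, 11, 15 and 18. This reproduces the list in Section 7.1.4: 6 doses per cycle, the last on Day 18.

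**Planned gaps.** 4−1 = 3, 8−4 = 4, 11−8 = 3, 15−11 = 4, 18−15 = 3, and 22−18 = 4. Every planned gap is 3 or 4 days.

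**Gap and dose counts for each permitted start.** The gap is S − 18. Cycle 2 XL888 days are S, S+3, S+7, S+10, S+14 and S+17. This assumes that cycle 2 runs from its actual Day 1, which the documents do not state.

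| Cycle 2 Day 1 | Gap after Day 18 (days) | XL888 doses, Days 1–21 | XL888 doses, Days 1–28 | Pembrolizumab, Days 1–21 | Pembrolizumab, Days 1–28 |
|---|---|---|---|---|---|
| Day 19 | 1 | 7 | 9 | 2 | 2 |
| Day 20 | 2 | 7 | 9 | 2 | 2 |
| Day 21 | 3 | 7 | 9 | 2 | 2 |
| Day 22 (planned) | 4 | 6 | 8 | 1 | 2 |
| Days 23–25 | 5–7 | 6 | 8 | 1 | 2 |

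Example for S = 19: cycle 2 doses fall on Days 19, 22, 26 and later. One is within 21 days (6+1 = 7) and three are within 28 days (6+3 = 9). The three doses on Days 15, 18 and 19 fall in 5 calendar days; the tightest planned run of three (Days 1, 4, 8) takes 8.

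**What depends on the assumption.** The gap and the 21-day counts do not. The 28-day count does. If only the first dose moved and the second cycle 2 dose stayed on Day 25, Days 1–28 would hold 6+2 = 8 XL888 doses, as planned.

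**Time left in the 21-day window after an early cycle 2 Day 1.** 21 − S = 2, 1 and 0 days for S = 19, 20 and 21.

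**After the change.** For escalation patients with S on Days 22 to 25, every start gives 6 XL888 and 1 pembrolizumab dose in Days 1–21, and 8 and 2 in Days 1–28. With a 3-day minimum elsewhere, the earliest next Day 1 after a Day 18 dose is 18+3 = Day 21.

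**The case against.** The strongest reply is that the protocol fixes XL888 at twice weekly (Table 2 and Sections 5.2.1 and 5.3.3), and three doses in a week is not twice weekly. A site could honour both statements by dropping or moving the Day 18 dose. That is a fair reading, but the text does not require it. Section 7.1.4 lists Day 18, Section 5.3.3 permits the early Day 1, and nothing says which yields. Two careful sites could dose differently.

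The early start is also optional, is meant for administrative reasons, and has no stated frequency. That stands. So does a limit on scope: Section 7.1.4 holds XL888 in cycle 1 for selected paired-biopsy patients, so they cannot have the short gap at the cycle 1–2 transition.

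A reader might infer that patients would be overdosed or that the RP2D would be biased. The documents do not support this. No dose is added to a cycle; one is moved forward by 1 to 3 days. The legible text gives no XL888 half-life or accumulation data from which to judge a 1-day gap. Three 90 mg doses total 270 mg, the same as two doses at the 135 mg single-agent capsule MTD in Section 4.1.2 (2 × 135 = 270). That does not show safety in combination or at a 1-day gap, but it gives no ground for alarm. For pembrolizumab, Section 4.1.1 reports on single-agent doses up to 10 mg/kg every 2 weeks: "All three dose levels were well tolerated and no dose-limiting toxicities were observed". The second pembrolizumab dose is therefore a question of uniform exposure. A dose given with 0 to 2 days of the window left has little time to produce a countable DLT, and several DLT clauses require toxicity to last for days.

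**Conclusion.** The point holds as a minor one. As written, the early side of the window permits a 1- or 2-day XL888 gap on a Day 19 or 20 start, shorter than any planned gap. A Day 21 start keeps a 3-day gap and is not a spacing problem. In dose-escalation patients, any start on Days 19 to 21 puts one more XL888 dose and one more pembrolizumab dose into the 21-day DLT window than planned.

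The arithmetic is firm, given that XL888 moves with the Day 1 visit and the Day 18 dose is taken. The clinical weight is not known: how often early starts would occur, and their effect on DLT rates, cannot be derived from the documents, and the effect is probably small. The case for change is that the plan allows a slightly worse schedule for no scientific gain and that the correction is easy.

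**What to change.** Amend Section 5.3.3, the flow chart window and Section 7.1.4 as follows.

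1. For dose-escalation patients, make the cycle 2 Day 1 window 0/+3 days, with no cycle 2 dose of either drug before Day 22. This gives uniform planned dose counts under both the 21-day and the 4-week DLT wording.
2. For all other cycles and patients, require at least 3 days between XL888 doses. If the Day 18 dose was taken, the earliest next Day 1 is then Day 21.

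No change to the compliance threshold in Sections 7.1.1.6 and 8.4 is needed. The cost is short edits in three places and slightly less scheduling freedom: escalation patients lose the early side of the window at cycle 2, and elsewhere a Day 19 or 20 start is ruled out once the Day 18 dose has been taken.

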### **5.3.4 Trial Blinding/Masking**

This is an open-label trial; therefore, the Sponsor, investigator and subject will know the treatment administered.

## **5.4 Concomitant Medications/Vaccinations (allowed & prohibited)**

Medications or vaccinations specifically prohibited in the exclusion criteria are not allowed during the ongoing trial. If there is a clinical indication for one of these or other medications or vaccinations specifically prohibited during the trial, discontinuation from trial therapy or

vaccination may be required. The investigator should discuss any questions regarding this with the PI. The final decision on any supportive therapy or vaccination rests with the investigator and/or the subject's primary physician.

#### **5.4.1 Acceptable Concomitant Medications**

All treatments that the investigator considers necessary for a subject's welfare may be administered at the discretion of the investigator in keeping with the community standards of medical care. All concomitant medication will be recorded on the case report form (CRF) including all prescription, over-the-counter (OTC), herbal supplements, and IV medications and fluids. If changes occur during the trial period, documentation of drug dosage, frequency, route, and date may also be included on the CRF.

All concomitant medications received within 28 days before the first dose of trial treatment and 30 days after the last dose of trial treatment should be recorded. Concomitant medications administered after 30 days after the last dose of trial treatment should be recorded for SAEs and ECIs as defined in Section 7.2.

#### **5.4.2 Prohibited Concomitant Medications**

Subjects are prohibited from receiving the following therapies during the Screening and Treatment Phase (including retreatment for post-complete response relapse) of this trial:

- Antineoplastic systemic chemotherapy, monoclonal antibody or biological therapy (including HSP90 inhibitors)
- Immunotherapy not specified in this protocol
- Investigational agents other than pembrolizumab and XL888
- Radiation therapy
  - Note: Radiation therapy to a symptomatic solitary lesion or to the brain may be allowed at the investigator's discretion. XL888 will be held will be held for 2 weeks before, during and 2 weeks after radiation.
- Live vaccines within 30 days prior to the first dose of trial treatment and while participating in the trial. Examples of live vaccines include, but are not limited to, the following: measles, mumps, rubella, varicella/zoster, yellow fever, rabies, BCG, and typhoid vaccine.
- Systemic glucocorticoids for any purpose other than to modulate symptoms from an event of clinical interest of suspected immunologic etiology. The use of physiologic doses of corticosteroids may be approved after consultation with the Sponsor.
- Inhibitors of CYP3A4 and/or PgP

Co-administration with strong inhibitors of CYP3A4 (e.g., ketoconazole, itraconazole, ritonavir) is prohibited.

- Co-administration with moderate CYP3A4 inhibitors (e.g., erythromycin, fluconazole) or PgP inhibitors should be avoided in the phase I portion. Co-administration with moderate CYP3A4 in the expansion portion can be done with caution and only if other alternatives are not available.
- Lists of CYP3A4 inducers and inhibitors can be found on: <http://medicine.iupui.edu/clinpharm/ddis/table.aspx> and <http://www.fda.gov/Drugs/DevelopmentApprovalProcess/DevelopmentResources/DrugInteractionsLabeling/ucm080499.htm> ).
- Seville orange, star fruit, grapefruit and their juices affect P450 and PgP activity and concomitant use with XL888 should be prohibited.
- Drugs that alter the gastric pH (eg, antacids, H2 receptor antagonists, and proton pump inhibitors) could reduce the solubility of XL888 in the GI tract and lower systemic exposure to XL888. Concomitant administration of these pH-altering drugs with XL888 should be avoided where possible and carefully documented otherwise.
- XL888 is highly protein bound in human plasma; thus, other drugs that are also highly protein bound should be avoided by subjects unless deemed clinically necessary, and the subject can be monitored for the desired drug effect or level and potential adverse effects. Examples of common medications that are also highly protein bound include warfarin, diazepam, furosemide, dicloxacillin, propranolol, and phenytoin.
- Inducers of CYP3A4 and/or PgP

Strong CYP3A4 inducers (i.e., phenytoin, carbamazepine, rifampin, rifabutin, phenobarbital, St. John's wort) are not allowed during the phase I portion. During the expansion phase, strong CYP3A4 inducers should only be used if alternatives are not available. Moderate inducers of CYP3A4 are allowed if alternatives are not available.

Subjects who, in the assessment by the investigator, require the use of any of the aforementioned treatments for clinical management should be removed from the trial. Subjects may receive other medications that the investigator deems to be medically necessary.

There are no prohibited therapies during the Post-Treatment Follow-up Phase.

